9.5. Efficacy Analysis

9.5.1. Primary Endpoint

The primary efficacy endpoint for this study is the categorical reduction in the daily OCS dose during weeks 20 to 24.

Percent reduction in the daily OCS dose will be categorized as follows:

- 90% to 100%
- 75% to <90%
- 50% to <75%
- >0% to <50%
- No decrease in OCS, loss of baseline asthma control during weeks 20 through 24, or discontinuation from study drug

Loss of baseline asthma control will be defined as FEV₁ less than 80% of baseline at the week 24 visit, clinically significant worsening in ACQ-6 score (change in score of 0.5) at the week 24 visit compared with baseline, and/or CAE during weeks 20 through 24.

9.5.2. Secondary Endpoints

The secondary efficacy endpoints for this study are the following:

- Proportion of patients achieving $\geq 50\%$ reduction in OCS dose at weeks 20 to 24 relative to the OCS dose at DoR/baseline, while maintaining asthma control
- Proportion of patients achieving dose reduction to ≤ 5 mg daily dose at weeks 20 to 24, while maintaining asthma control
- Percent change from DoR/baseline in OCS dose at weeks 20 to 24
- Proportion of patients achieving less than 5 mg decrement in OCS dose (ie, the minimal and non-responders) compared with the OCS dose at DoR/baseline at weeks 20 to 24, while maintaining asthma control
- Clinical asthma exacerbation-related:
 - Annualized rate of CAEs requiring a burst of systemic corticosteroid (injection, or if oral, at least a doubling from the current OCS dose for at least 3 days); an asthma-specific hospital admission; or an asthma-specific emergency department visit during the treatment period (weeks 0 to 24)
- Proportion of patients discontinuing OCS at weeks 20 to 24, while maintaining asthma control

The order of the secondary endpoints above is the order of hierarchy to be used for controlling type I error as described in Section [9.6](#).

[figure not shown]
9.5.3. Other Secondary Efficacy Endpoints:

Other efficacy endpoints for this study are the following:

- Time to first CAE
- Other clinic lung functions including the following:
 - Pre-bronchodilator FEV₁: change from DoR/baseline to weeks 4, 8, 12, 16, 20, and 24 or early withdrawal
 - Post-bronchodilator FEV₁: change from DoR/baseline to weeks 4, 12, 20, and 24 or early withdrawal
- Ambulatory lung function: change in AM and PM PEF from run-in baseline at each week through week 24 or early withdrawal
- AQLQ + 12 score: change from DoR/baseline to weeks 4, 8, 12, 16, 20, and 24 or early withdrawal
- ACQ-6: change from DoR/baseline to weeks 4, 8, 12, 16, 20, and 24 or early withdrawal
- Change in total inhalations of reliever bronchodilator medication (eg, SABA) (number of inhalations per 24 hours: day+night) from run-in baseline at each week through week 24 or early withdrawal
- Number of nighttime awakenings due to asthma over the 24-week treatment period
- Change in total asthma symptom scores from run-in baseline at each week through week 24 or early withdrawal
- EQ-5D score: change from DoR/baseline to week 24 or early withdrawal
- SGRQ score: change from DoR/baseline to weeks 12 and 24 or early withdrawal

9.5.4. Exploratory Endpoints

Exploratory endpoints for this study are the following:

9.5.5. Target Biomarker Endpoint

The target biomarker endpoints are the blood eosinophil counts at DoR/baseline; weeks 4, 8, 12, 16, 20, 24 or early withdrawal; and at the follow-up visit (approximately week 32).

9.5.6. Planned Method of Analysis

The ITT analysis set (see Section 9.2.1) will be used for all efficacy analyses unless otherwise noted. Summaries will be presented by treatment group. The per-protocol analysis set will be used as sensitivity analysis for the primary analysis.

9.5.6.1. Primary Efficacy Analysis

The primary endpoint is the categorical reduction in OCS dose during weeks 20 to 24, compared with DoR/baseline dose, without loss of asthma control. Five categories of reduction will be defined: 90% to 100% reduction, 75% to <90% reduction, 50% to <75% reduction, >0% to <50% reduction, and no decrease in OCS dose/loss of asthma control/discontinuation from study drug. This categorical endpoint will be analyzed using proportional odds model. The model will include the treatment group and randomization stratification factors as model factors and the OCS baseline dose and duration of historical OCS use (ie, before screening) as covariates. The overall odds ratio between reslizumab and placebo and its 95% confidence interval will be estimated.

For the primary analysis, patients who discontinue the study drug early will be considered as nonresponders and will be categorized in the lowest category of response.

If a patient elects to withdraw (or is discontinued from treatment by the investigator), every attempt will be made to continue the assessments subsequent to his/her withdrawal from the study (see Section 4.5).

9.5.6.2. Sensitivity Analysis

Sensitivity analysis will include data collected after early discontinuation from study drug. In this analysis, patients will be categorized according to the percent dose reduction at 24 weeks regardless of whether they withdrew early from treatment or complete treatment. For patients who withdraw early, and for whom the sponsor fails to retrieve data after withdrawal despite all attempts to contact the patients, multiple imputation will be performed to determine the categorization according to the percent dose reduction at 24 weeks. Multiple imputations will use the post withdrawal data observed for patients who withdraw early and for which the sponsor succeeded to retrieve the data. The methodology and algorithm to be used for imputations will be detailed in the statistical analysis plan.

Other sensitivity analyses will include the following:

- Repeating the primary analysis on the PP analysis set
- “Tipping point” multiple imputation analysis to assess deviations from missing at random (MAR); details regarding this analysis will be provided in the SAP

Additional sensitivity analyses may be included and will be detailed in the statistical analysis plan.

9.5.6.3. Secondary Efficacy Analysis

All efficacy variables will be summarized by treatment group. For continuous variables, the summary statistics will include n, mean, SD, SE, median, minimum, and maximum. For categorical variables, patient counts and percentages will be provided.

The proportion of patients achieving $\geq 50\%$ reduction in OCS dose at weeks 20 to 24 while maintaining asthma control, proportion of patients achieving dose reduction to ≤ 5 mg daily dose at weeks 20 to 24 while maintaining asthma control, proportion of patients achieving less than 5 mg decrement in OCS dose (ie, the minimal and non-responders) at weeks 20 to 24 while maintaining asthma control, and proportion of patients discontinuing OCS at weeks 20 to 24 will be analyzed using a logistic regression model. The model will include the treatment group and randomization stratification factors as model factors and the OCS baseline dose and duration of historical OCS use (ie, before screening) as covariates.

For the secondary analysis, patients who discontinue the study drug early will be considered as nonresponders and will be categorized in the lowest category of response

Analysis of the mean percentage change from baseline in OCS dose at weeks 20 to 24 will use an analysis of covariance model with treatment group and stratification factors as model factors and the OCS baseline dose and duration of historical OCS use (ie, before screening) as covariates.

The frequency of CAEs will use the negative binomial (NB) regression model. The primary NB model will include the treatment group and randomization stratification factors as model factors and an offset variable. The offset variable will be calculated as the logarithm of follow-up duration minus the summed duration of exacerbations. The ratio of CAE rate between the treatment groups and its 95% confidence interval (CI) will be estimated from the NB model.

Additional covariates or factors may be added to the statistical models. These will be detailed in the statistical analysis plan.

9.5.6.4. Other Efficacy Analysis

Statistical modeling to be used for other efficacy endpoints will be described and detailed in the statistical analysis plan.

9.5.6.5. Exploratory Efficacy Analysis

Statistical modeling to be used for exploratory efficacy endpoints will be described and detailed in the statistical analysis plan.

9.6. Multiple Comparisons and Multiplicity

A fixed sequence multiple testing procedure will be implemented to test the primary and secondary variables while controlling the overall type I error rate at 0.05. If the resulting 2-sided p-value from the primary comparison is ≤ 0.05 , then the next comparison of interest (first secondary variable) will be interpreted inferentially at 0.05. This process continues through the secondary variables either until all comparisons of interest are interpreted inferentially or until

the point at which the resulting 2-sided p-value for a comparison of interest is >0.05 . At the point where $p>0.05$, no further comparisons will be interpreted inferentially. The hierarchy of endpoints is as defined in Section 9.5.2.

No multiplicity adjustments will be made for other efficacy and exploratory efficacy analyses.

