6.3.1. Secondary Variables

The secondary efficacy endpoints for this study are as follows:

- Proportion of patients achieving $\geq 50\%$ reduction in OCS dose at weeks 20 to 24 relative to the OCS dose at the date of randomization (DoR)/baseline, while maintaining asthma control

- Proportion of patients achieving dose reduction to ≤ 5 mg daily dose at weeks 20 to 24, while maintaining asthma control
- Percent change from DoR/baseline in OCS dose at weeks 20 to 24
- Proportion of patients achieving less than 5 mg decrement in OCS dose (ie, the minimal and non-responders) at weeks 20 to 24 compared with the OCS dose at DoR/baseline, while maintaining asthma control
- Annualized rate of clinical asthma exacerbations requiring a burst of systemic corticosteroid (injection, or if oral, at least a doubling from the current OCS dose for at least 3 days); an asthma-specific hospital admission; or an asthma-specific emergency department visit during the treatment period (weeks 0 to 24)
- Proportion of patients discontinuing OCS at weeks 20 to 24, while maintaining asthma control

Testing of the secondary variables will be performed using the sequential testing procedure in the order specified above, as described in Section 4.3.

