6.3.3.2. Analysis

The annualized rate of CAEs will be analyzed using the generalized linear model (GLM) for data from the negative binomial distributions, commonly referred to as the negative binomial (NB) regression model. The NB model will include factors for treatment group, randomization strata (age and OCS dose as defined in Section 2.4), number of exacerbations in the previous year, and an offset variable. The offset variable will be calculated as the logarithm of follow-up duration minus the summed duration of exacerbations during the follow-up. Age and OCS dose will be based on data recorded in the clinical database.

The ratio of CAE rate between the treatment groups and its 95% CI will be estimated from the NB model. Treatment effect will be evaluated using the likelihood based chi-square test. The analysis of clinical asthma exacerbations will be on-treatment, excluding exacerbations observed after stopping study treatment. For patients who complete treatment, the treatment period will be defined from the first dose of study drug to the end of treatment (week 24) visit. For patients who prematurely discontinue treatment, the treatment period will be defined from the first dose of study drug to the last dose of study drug + 4 weeks. Analyses will only be performed if a sufficient number of patients have exacerbations for the model to converge satisfactorily.

The following sample SAS[®] code pertains to the analysis of CAEs.

```
proc genmod data=<<>>;
  class treatment strata1 strata2;
  model cae=treatment strata1 strata2 nexac /dist=negbin link=log offset=log_futime;
  estimate "CAE rate ratio" treatment 1 -1;
  lsmeans treatment /diff exp cl;
  ods output lsmeans=<<>>;
  ods output lsmeandiffs=<<>>;
run;
```

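### SAP 6.3.3.2 can drop the gated exacerbation-rate test on an undefined convergence condition, with no fallback and no rule for the endpoint behind it

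*Protocol*

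**What the plan says.** Protocol 9.5.2 lists six secondary endpoints, with the annualized CAE rate fifth and OCS discontinuation sixth, and adds: "The order of the secondary endpoints above is the order of hierarchy to be used for controlling type I error". SAP 6.3.1 repeats the list and the rule: "Testing of the secondary variables will be performed using the sequential testing procedure in the order specified above".

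Protocol 9.6 and SAP 4.3 set out a fixed-sequence procedure "controlling the overall type I error rate at 0.05". It has two branches. At p ≤ 0.05 the next comparison is interpreted inferentially, and in the protocol's words: "This process continues through the secondary variables either until all comparisons of interest are interpreted inferentially". At p > 0.05, "no further comparisons will be interpreted inferentially".

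For the CAE rate, Protocol 9.5.6.3 names the method without any condition: "The frequency of CAEs will use the negative binomial (NB) regression model". SAP 6.3.3.2 keeps that model, with treatment, the age and OCS-dose strata, previous-year exacerbations and an offset, and then adds: "Analyses will only be performed if a sufficient number of patients have exacerbations for the model to converge satisfactorily". By its Introduction, the SAP prevails where the two differ. SAP Table 13, which lists changes from the protocol's analyses, records only the added covariate and not this condition.

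**The concern.** The condition can remove a p-value from a sequence that is defined only in terms of p-values. The SAP gives no minimum number of patients with events, no meaning for satisfactory convergence, no alternative model, and no time or blinding status for the decision.

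Two things are at stake. The CAE rate, a confirmatory endpoint, can go untested although its data would support a valid test. And OCS discontinuation, the only comparison behind it, is left without a stated status: the text says neither that the sequence stops nor that it moves on.

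The SAP handles similar matters more firmly elsewhere. The repeated-measures model in 6.3.2.2.1 has an ordered list of covariance structures to try if the fit fails, and a minimum of 15 patients per group. Per-protocol exclusions (3.3.1) rest on review of blinded data, and the steroid conversion table (6.3.2.2.3) is settled before unblinding. The gated CAE test has no comparable safeguard.

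**Working it through.** **1. The plan's own figure.** The only stated sample-size figure is for the primary endpoint: 76 per group for 90% power, odds ratio 2.63, two-sided 0.05 (Protocol 9.1). With Whitehead's proportional-odds formula, n per group = 6(z₀.₉₇₅ + z₀.₉₀)² / [(ln 2.63)² (1 − Σp̄³)]. The placebo distribution 10.9/7.9/14.8/10.8/55.6% and an odds ratio of 2.63 imply 24.3/13.5/19.3/10.6/32.3% on reslizumab, so Σp̄³ = 0.0976. Then n = 6 × 10.507 / (0.9351 × 0.9024) = 74.7, or 75 against the stated 76; power at 76 is 90.5% by formula and 89.9% by simulation. The figure reproduces. It says nothing about the CAE rate, for which the documents give no rate, dispersion or power, and they give no planned number of adolescents.

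**2. The rule and the condition side by side.**

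| CAE result | Protocol 9.6 / SAP 4.3 |
|---|---|
| p ≤ 0.05 | go on to OCS discontinuation |
| p > 0.05 | stop |
| analysis not performed (SAP 6.3.3.2) | not covered |

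**3. How often the fit might fail.** Because the documents give no inputs, these are ranges under assumptions, with 152 patients followed for 24 weeks.

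- Simulation A: rate ratio 0.6, dispersion 0.8, 200 runs per cell. Unsatisfactory means optimiser failure, or any coefficient standard error that is infinite or at least 10.

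| Placebo CAEs per year | 0.1 | 0.3 | 0.6 | 1.0 | 2.0 |
|---|---|---|---|---|---|
| No age term | 63% | 25% | 11% | 3% | 0% |
| 8 adolescents | 90% | 53% | 25% | 7% | 0.5% |
| 3 adolescents | 97% | 80% | 61% | 43% | 19% |

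- With 3 adolescents most failures arise because that stratum has no events.
- Simulation B: rate ratio 0.5, age term kept, 3 or 8 adolescents, 0.6 to 1.5 CAEs per year. Unsatisfactory fits occurred in about 18% to 72% of runs. In those runs a Poisson model with robust variance always gave a finite treatment p-value, and it was significant in 37% to 76% of them.

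The spread shows how strongly the answer depends on the event rate, the adolescent count and what is called unsatisfactory. The SAP fixes none of these.

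**4. Type I error for the last two tests.** Take all earlier tests as passed and both remaining hypotheses as null.

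- Missing p-value stops the sequence: at most 0.05.
- CAE test omitted by a rule independent of the results, for example a pooled event count: 0.050 whatever the omission probability.
- CAE test set aside in a fraction f of its non-significant results, independent tests: 0.05 + 0.95 × f × 0.05. This gives 0.055 at f = 0.1, 0.074 at f = 0.5, and 1 − 0.95² = 0.0975 at f = 1. The f = 1 value falls to 0.095 at correlation 0.3 and 0.088 at correlation 0.6.

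**The case against.** The best case for the plan is that this is an ordinary sparse-data proviso. It speaks of too few patients with exacerbations, not of an unwelcome p-value. A fit that yields p > 0.05 triggers the written stop rule. The sequence licenses the next comparison only when the preceding p-value is at most 0.05, so on a natural conservative reading a missing p-value simply ends testing. The condition bites only if all five earlier tests succeed, and at 1 CAE per year or more, without a very small age stratum, Simulation A puts failure at 0% to 7%.

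Much of this stands, and it rules out three stronger readings.

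- A reader might infer that the plan inflates type I error to 9.75%. That needs the test to be set aside because of its observed result, which nothing in the SAP provides for.
- A reader might infer that a dispersion estimate of zero, common with mildly overdispersed counts, removes the test. It does not in itself: at zero dispersion the negative binomial likelihood equals the Poisson likelihood, so the likelihood-based chi-square test in SAP 6.3.3.2 is still defined. In 400 null runs at each of three dispersions (1 CAE per year, no age term) it gave a finite p-value every time. How often the dispersion estimate reaches zero is therefore not how often the test is lost.
- A reader might infer that the decision must follow unblinding. The fit of a model containing treatment does need the codes, but the number of patients with events could be counted pooled and blinded. The documents do not say which is meant.

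What the objection leaves untouched is that the conservative reading is not written down, and that it would still lose a CAE test the data could support.

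**Conclusion.** The point holds, within limits. A written rule allows the fifth of six confirmatory secondaries to be dropped on an undefined criterion with no fallback, and the sequence rule does not cover the outcome. Only the CAE rate and OCS discontinuation are exposed; the primary endpoint and secondaries 1 to 4 are not.

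The main cost is a lost test. The risk is concentrated where events are few or the adolescent stratum has none, and it is small at higher rates with a reasonably filled stratum. All frequencies rest on assumed CAE rates, rate ratios and adolescent counts. For type I error the documents establish a gap in the rule, not a breach: the level stays at 0.05 under either orderly way of handling the missing p-value, and 9.75% is an upper bound for a discretionary omission that the plan does not describe. This should be corrected before unblinding.

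**What to change.** In SAP 6.3.3.2, delete the sentence that makes the gated CAE analysis conditional and put an ordered fallback in its place:

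1. Fit the negative binomial model as specified.
2. If it does not converge, and either age stratum has no events, drop the age factor and refit. The event check is made on pooled data and needs no treatment codes.
3. If it still does not converge, or the dispersion estimate is at zero and standard errors are not obtained, fit a Poisson regression with the remaining terms, the same offset and a robust (sandwich) variance. Its two-sided p-value is then the gate.

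Say what non-convergence means, for instance the status reported by the fitting procedure. Dropping the age factor comes first because a Poisson model that kept it would have the same unidentifiable coefficient when that stratum has no events.

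In Protocol 9.6 and SAP 4.3, add that the sequence stops at any comparison that yields no p-value. That sentence alone closes the type I error gap; the fallback keeps a usable CAE test from being lost.

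The cost is a few sentences and one or two extra model calls, with no added patients or data. The small downside is that a different model or variance estimator may supply the gated p-value. A two-step version (negative binomial likelihood-ratio test, robust Poisson at zero dispersion) rejected in 4.3% to 5.6% of simulated null trials. Those runs had no age term, so the age-dropping step should be simulated before the SAP is amended.

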9.7. Safety Endpoints and Analysis

Safety analyses will be performed on the safety analysis set.

9.7.1. Safety Endpoints

Safety measures and time points are provided in Section 3.8 and Table 5. The overall safety of reslizumab treatment will be assessed throughout the study by evaluating adverse events and the following additional safety variables.

- Clinical laboratory evaluations of serum chemistry at screening, DoR, week 12, and week 24 or early withdrawal
- Clinical laboratory evaluations of hematology throughout the study
- Vital signs assessments (pulse, body temperature, respiratory rate, and blood pressure) throughout the study
- ECGs at screening and week 24 or early withdrawal
- Physical examinations (including body weight measurements) throughout the study
- Signs and/or symptoms of adrenal insufficiency (OCS withdrawal effects) throughout the study
- Inquiries about concomitant medication usage throughout the study

9.7.2. Safety Analysis

Safety data will be summarized using descriptive statistics by time point and/or treatment group, as appropriate.

All adverse events will be coded using the Medical Dictionary for Regulatory Activities (MedDRA). Each patient will be counted only once in each preferred term or system organ class category for the analyses of safety. Summaries will be presented for all adverse events starting after first study drug administration (overall and by severity), adverse events determined by the investigator to be related to study treatment (ie, reasonable possibility; see Section 7.1.4, with missing relationship will be counted as related) (overall and by severity), serious adverse events, adverse events causing discontinuation from study treatment, adverse events with onset during the follow-up period (ie, after the cessation of study treatment), and adverse events that begin within 24 hours after injection. Summaries will be presented by treatment group and for all patients. Patient listings of adverse events, serious adverse events, and adverse events leading to discontinuation will be presented and will include all adverse events reported (including before first study drug administration).

Changes in laboratory, ECG, and vital signs measurement data will be summarized descriptively. All values will be compared with prespecified boundaries to identify potentially clinically significant changes or values, and such values will be listed.

The use of concomitant medications coded with WHO Drug will be summarized by therapeutic class using descriptive statistics. Concomitant medications will include all medications taken while the patient is treated with study drug.

For continuous variables, descriptive statistics (n, mean, SD, SE, median, minimum, and maximum) will be provided for actual values and changes from baseline to each time point. For categorical variables, patient counts and percentages will be provided.

If any patient dies during the study, a listing of deaths will be provided and all relevant information will be discussed in the patient narrative included in the clinical study report.

